## 7. Possible Discomforts and Risks:

### **Blood draw:**

The risks of drawing blood from a vein include discomfort at the site of puncture; possible bruising and swelling around the puncture site; rarely an infection; and, uncommonly, faintness from the procedure. The risk from a blood draw is considered to be minimal.

### **Study medication:**

Eplerenone is a Food and Drug Administration approved medication for treatment of hypertension. Eplerenone was documented to be safely tolerated among patients with moderate to severe asymptomatic aortic stenosis. This medication can increase serum

potassium which will be monitored at baseline, 1 week and 4 weeks after initiation. Possible adverse reactions include: headache, dizziness, diarrhea, stomach pain, chest pain, nausea, cough or flu-like symptoms (such as fever, chills, body aches, or unusual tiredness), vaginal bleeding, breast swelling/tenderness, or rash.

**Questionnaire:** Possible emotional discomfort when answering some of the questions; however, this risk is exceeding small.

**Confidentiality:** Confidential information about subjects might be accidentally disclosed. We will use our best efforts to keep the protected health information secure. The risk of accidental disclosure is exceeding small.

#### **8. Possible Benefits:**

Subjects might breath better, have more energy, and have better control of their blood pressure from taking eplerenone. Subjects might also enjoy the satisfaction of participating in a research project that could ultimately help others.

#### **9. Conflict of Interest:**

No conflict of Interest

5/14/2020

NCT03923530

IRB 201901097

Pressure Assessment to Improve Outcomes after TAVR:
a registry

IRB 201901097

Pressure Assessment to Improve Outcomes after TAVR: a registry

5/14/2020

NCT03923530

- 1.
2. We used Kolmogorov-Smirnov and Shapiro-wilk tests to examine distribution of our data. Despite small sample size, we had normal distribution. Therefore, we used parametrical approaches to compare means before and after the TAVR.
3. We used descriptive analysis to calculate Mean and standard deviation for age of the patients.
4. We used paired t-test to compare mean Kansas City Cardiomyopathy Questionnaire parameters, including physical limitation, symptom frequency, quality of life, social limitation, and overall summary before and after TAVR. We employed the paired t-test to compare mean of left ventricular end diastolic pressure, systolic and diastolic blood pressures before and after TAVR as well.
5. P value less than 0.05 was considered as statistically significant.
6. All statistics were done by SPSS software, version 24 (IBM Corp., Armonk, NY, USA).

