## **5. Specific Aims:**

- 1) Determine the tolerability of eplerenone among patients with abnormal hemodynamics and hypertension after TAVR.
- 2) Determine the feasibility of administering the KCCQ-12 at baseline and 8 weeks to assess quality of life.

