## **6. Research Plan:**

- 1) Enroll 25 subjects with hypertension and abnormal hemodynamics after TAVR.
- 2) Enrollment for non-local subjects will occur remotely with telephonic consent and mailing of the questionnaire and study drug. Enrollment for local subjects will occur remotely or in-person.
- 3) This is a greater than minimal risk study.
  - a. Inclusion criteria:
    - i. TAVR procedure performed at the Malcom Randall VA Medical Center within the last 2 years.
    - ii. Intracardiac pressures recorded 5 to 10 minutes after TAVR and AVi < 0.6 mm Hg/bpm.
    - iii. History of hypertension, taking anti-hypertensive medications, or recent systolic blood pressure  $\geq$ 130 mm Hg.
  - b. Exclusion criteria:
    - i. Serum potassium >5.5 mEq/L at initiation.
    - ii. Concomitant administration of strong CYP3A inhibitor (i.e. ketoconazole, itraconazole, nefazodone, troleandomycin, clarithromycin, ritonavir, and nelfinavir).
    - iii. Serum creatinine >2.0 for men and >1.8 for women.
    - iv. Creatinine clearance <50 cc/min.
    - v. Concomitant administration of potassium supplements or potassium-sparing diuretics.

- 4) Subjects who are eligible to participate and signed an informed consent will be given eplerenone 50 mg daily. Study drug (eplerenone) will be paid by the North Florida Foundation for Research and Education for the duration of the study.
  - a. Down-titration or termination of non-essential anti-hypertensive agents is permissible so that eplerenone does not result in hypotension. Essential medications are as follows:
    - i. Angiotensin converting enzyme inhibitors (ACE-inhibitors) or angiotensin receptor blockers, if intolerant to ACE-inhibitors are indicated for treatment left ventricular dysfunction (i.e. left ventricular ejection fraction  $\leq 40\%$ ), diabetes, and proteinuric chronic kidney disease.
    - ii. Beta-blockers are indicated 3 years after an acute myocardial infarction, unless there is persistent left ventricular dysfunction (i.e. left ventricular ejection fraction  $\leq 40\%$ ).
- 5) Monitoring.
  - a. Serum potassium within the last 30 days is required before initiating eplerenone. Repeat blood draw is required within the first week, and one month after the start of treatment with eplerenone.
  - b. An order will be placed for the blood draws to be performed at the subject's local VA community-based outpatient clinic or hospital.

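### The SAP was written after the data were examined and applies a 0.05 threshold to eight paired t-tests with no primary endpoint fixed in advance

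*SAP*

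**What the plan says.** SAP item 2 begins "We used Kolmogorov-Smirnov and Shapiro-wilk tests to examine distribution of our data". It then gives the outcome of that check, "Despite small sample size, we had normal distribution", and the consequence, "Therefore, we used parametrical approaches to compare means before and after the TAVR". Item 4 applies paired t-tests to the KCCQ parameters, listed as "physical limitation, symptom frequency, quality of life, social limitation, and overall summary before and after TAVR", and to the "mean of left ventricular end diastolic pressure, systolic and diastolic blood pressures before and after TAVR as well". Item 5 sets the threshold: "P value less than 0.05 was considered as statistically significant". The SAP is dated 5/14/2020. It names no primary endpoint, sidedness, multiplicity method, analysed sample size or data-lock date.

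The available protocol text has no statistical section. Its first aim (section 5) is "Determine the tolerability of eplerenone among patients with abnormal hemodynamics and hypertension after TAVR"; the second is whether the KCCQ-12 can feasibly be administered at two time points. Section 6, item 1 gives the size, "Enroll 25 subjects with hypertension and abnormal hemodynamics after TAVR", without a power or precision basis.

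**The concern.** A document that states how the data turned out was written after someone looked at them. That holds whatever its date, and items 2 to 6 are all in the past tense. Filed as an SAP with a significance rule, it invites the reader to treat each P<0.05 as the result of a test fixed beforehand. Nothing in the available protocol fixes one: neither aim is a hypothesis about mean change, and no outcome is ranked above the others.

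The protocol's Abstract and Background say the registry prepares for a pilot randomized trial of eplerenone against placebo. A significant before-after change in a KCCQ score or a pressure, read as pre-specified, would look like firmer support for that trial than it is.

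**Working it through.** **1. Can the tested outcomes be traced to the protocol?**

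| SAP outcome | Tests | In the protocol |
|---|---|---|
| KCCQ: four domains | 4 | Background names the same four domains; section 6, item 6 schedules the KCCQ-12 at enrolment and week 8 |
| KCCQ: overall summary | 1 | Only through the instrument |
| Systolic and diastolic pressure | 2 | Section 6, item 5c schedules a reading at week 8 |
| LVEDP | 1 | Intracardiac pressures after TAVR are an eligibility item (section 6, inclusion criterion ii); no follow-up measurement |

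That makes 4 + 1 + 2 + 1 = 8 tests. Seven concern planned measures and one (LVEDP) does not. The protocol plans a hypothesis test on none of the eight.

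**2. Does choosing the t-test after a normality check damage its 5% error?** Hardly. If the paired differences are normal, the Shapiro-Wilk statistic does not depend on location or scale, so by Basu's theorem it is independent of the t statistic. Passing the check leaves the t-test's size unchanged. Simulation (20,000 samples, N = 25, normal differences, no true change) gives:
- t-test always: 5.2%
- t-test among samples that passed Shapiro-Wilk: 5.2%
- Shapiro-Wilk, then t or Wilcoxon: 5.4%

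The check is also weak evidence of normality at this size. Against a skewed gamma distribution (shape 2, assumed), Shapiro-Wilk at 0.05 rejects only 24%, 37% and 65% of the time at N = 10, 15 and 25.

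**3. What does the lack of a primary endpoint allow?** The SAP states no family-wise figure, so there is none to reproduce. Inputs: 8 tests (item 4), 0.05 per test (item 5, taken as two-sided), planned N = 25 (protocol section 6). The correlation between outcomes is not given and is assumed.

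- Upper bound: 8 × 0.05 = 0.40.
- Independent outcomes: 1 − 0.95^8 = 1 − 0.663 = 0.337.
- Correlated outcomes: 20,000 simulated samples per cell, equal correlation, no true change. Entries are the chance of at least one P<0.05.

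| Correlation | N = 10 | N = 15 | N = 25 |
|---|---|---|---|
| 0 | 34.0% | 33.0% | 33.7% |
| 0.3 | 31.0% | 30.1% | 30.1% |
| 0.5 | 26.4% | 25.0% | 25.6% |
| 0.7 | 20.9% | 20.1% | 19.4% |
| 0.9 | 12.9% | 12.6% | 12.5% |

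The analysed N is unknown but matters little; the correlation drives the result. The five KCCQ tests alone, if independent, give 1 − 0.95^5 = 0.226.

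**The case against.** The strongest reply has three parts. First, the SAP nowhere claims to be pre-specified or confirmatory. Its past tense is open about its timing, the study is called a registry, and no passage makes the pilot depend on a significant result. Second, most of the tested variables are ones the protocol set out to measure. Third, item 5 does state an error rate, 0.05 for each test, and an earlier analysis plan may exist outside these documents.

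Much of this stands. A reader might infer that the outcomes were chosen because of their results. The documents show when the SAP was written and that the parametric tests followed from the normality check; they do not show what drove the outcome list, and step 1 of the working counts against that inference. A reader might also infer that several tests were tried and the smallest p-value kept. With 25 pairs that would give about 6% for the better of t and Wilcoxon, and 7% to 8% with a sign test added. But the SAP mentions neither alternative, so those figures do not describe this plan.

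The reply does not supply a primary endpoint or a pre-specified comparison, and it does not explain why a retrospective account should carry an unqualified significance rule. Planning to measure a variable is not the same as planning to test its mean change.

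**Conclusion.** The point holds as a matter of labelling and interpretation. The SAP is retrospective, its choice of tests rests on inspected data, and its eight mean-change tests are not pre-specified in the available documents. With no true change, the chance of at least one P<0.05 is about 12% to 34%. This assumes eight two-sided tests, N = 25, normal differences, and equal correlation from 0.9 down to 0. The exposure comes from the number of tests without a primary endpoint, not from the normality check.

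It does not follow that the outcomes were selected for significance or that any single reported p-value is wrong. The conclusion would change if an earlier dated plan named a primary endpoint, or if SAP item 1, which is blank in the copy read, contains one.

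One related matter needs its own resolution. The SAP describes its comparisons as before and after TAVR, whereas the protocol's questionnaire schedule starts at enrolment, when TAVR has already been done. The account of planned measures above concerns the variables, not those time points.

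**What to change.** Four changes to the SAP:

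1. State at its head that it was written after the data were examined, and give the data-lock date.
2. Replace item 5 with: *All mean-change comparisons are exploratory; mean change with 95% confidence interval is reported, and no p-value is taken as confirmatory evidence.*
3. Label the LVEDP comparison post hoc.
4. Note that the KCCQ-12 and blood pressure were planned measures but that their tests were not pre-specified.

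If an earlier dated analysis plan exists, file it and mark each departure from it.

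A Bonferroni threshold is not a substitute. 0.05/8 = 0.00625 would cap the family-wise error at 5%, but would raise the change detectable with 80% power at N = 25 from 0.58 to 0.78 SD, and would not make the tests pre-specified.

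The cost is wording only, with no new data or analyses beyond the intervals. The sponsor gives up confirmatory use of the term statistically significant.

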  - c. Blood pressure will be recorded in the research office for local subjects and through the primary care provider for non-local subjects at 8 weeks.
- 6) Quality of life questionnaire.
  - a. The Kansas City Cardiomyopathy Questionnaire (KCCQ-12) will be administered at baseline and 8 weeks. The KCCQ-12 instrument will be mailed to all subjects. Local subjects will be given the opportunity to complete the questionnaire in the research office, if they prefer. Study coordinator will call the subject at 8 weeks to confirm vital status, assess if any adverse reactions from eplerenone, and provide assistance to completing the KCCQ-12, if needed.

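### The SAP labels all eight named paired t-tests as before versus after TAVR, but both KCCQ-12 forms come after TAVR and no pair is scheduled for LVEDP or blood pressure

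*SAP*

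**What the plan says.** SAP item 2 sets the general approach: "we used parametrical approaches to compare means before and after the TAVR". Item 4 applies it to five KCCQ scores, the last three being "quality of life, social limitation, and overall summary before and after TAVR", and then to the "mean of left ventricular end diastolic pressure, systolic and diastolic blood pressures before and after TAVR as well". Item 5 attaches a 0.05 significance threshold.

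The protocol describes a different sequence. Inclusion criterion i (6. Research Plan, item 3a) requires a "TAVR procedure performed at the Malcom Randall VA Medical Center within the last 2 years", and criterion ii requires "Intracardiac pressures recorded 5 to 10 minutes after TAVR and AVi < 0.6 mm Hg/bpm". Eligible, consented subjects then receive eplerenone (item 4). Aim 2 is to "Determine the feasibility of administering the KCCQ-12 at baseline and 8 weeks to assess quality of life", and Research Plan item 6a repeats the schedule: "The Kansas City Cardiomyopathy Questionnaire (KCCQ-12) will be administered at baseline and 8 weeks". On blood pressure, item 5c says "Blood pressure will be recorded in the research office for local subjects and through the primary care provider for non-local subjects at 8 weeks".

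**The concern.** A paired test needs two values per subject, and its label must name what happened between them. In this protocol the valve has already been replaced when a subject consents, and eplerenone is what starts between the two questionnaires. The SAP names the valve procedure instead.

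The registry is meant to set the stage for a randomized trial of eplerenone against placebo. If the KCCQ results are read as the SAP labels them, a change seen while patients take eplerenone is credited to TAVR, and the planned trial loses the quality-of-life information it was meant to get. For LVEDP and blood pressure, a reader could not tell whether a result describes the procedure, the drug period or both. These t-tests do not decide tolerability, but they are the only outcome comparisons in the visible SAP.

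**Working it through.** The documents give no effect size, SD or power figure for these comparisons, so there is no calculation to reproduce. The check sets each named test against the protocol's schedule.

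**Count of tests (SAP item 4).** 5 KCCQ scores + 1 LVEDP + 2 blood pressures = 8.

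**Scheduled values for each test.**

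| Measure | Tests | Scheduled before TAVR | Scheduled or specified after TAVR | Scheduled pair across TAVR | Scheduled pair across eplerenone |
|---|---|---|---|---|---|
| KCCQ-12 scores | 5 | none | study baseline; 8 weeks | no | yes |
| LVEDP | 1 | none | 5 to 10 minutes after TAVR | no | no |
| Systolic BP | 1 | none | 8 weeks | no | no |
| Diastolic BP | 1 | none | 8 weeks | no | no |

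Totals:
- scheduled value before TAVR: 0 of 8;
- scheduled pair over the eplerenone period: 5 of 8;
- no scheduled pair under either reading: 3 of 8.

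**Other pressures mentioned.** The AVi uses an aortic end-diastolic pressure, but from the same post-TAVR recording. A recent systolic pressure is one of three alternative ways to meet inclusion criterion iii. It is therefore not required of everyone, has no date window and has no diastolic counterpart. Neither is planned as a comparator.

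**How far the KCCQ label can be from the truth.** Assume the 2-year entry window is counted to the baseline form.
- Baseline form: up to 2 × 52 = 104 weeks after TAVR.
- 8-week form: up to 104 + 8 = 112 weeks after TAVR.

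So the score labelled as pre-procedure can be about two years post-procedure.

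**Could it be one stray word?** The TAVR label appears three times in the SAP (once in item 2, twice in item 4). The words eplerenone, baseline and weeks do not appear there at all.

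**If pre-TAVR pressures were found in records.**
- A pre-TAVR blood pressure paired with the 8-week value would span both the procedure and the drug.
- A procedural LVEDP contrast would be made in subjects chosen for AVi below 0.6 mm Hg/bpm. The AVi is the aortic-minus-ventricular end-diastolic difference divided by heart rate, so the post-TAVR LVEDP is part of the selection rule.

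**The case against.** The strongest reply is that the pressures differ from the KCCQ. A protocol that enrols after TAVR cannot prospectively schedule any pre-TAVR value, so for LVEDP and blood pressure the zero count partly restates the entry criterion. The Background refers to pressures obtained at the time of TAVR, and a procedural before/after contrast from existing records would be coherent. The SAP is written in the past tense, which suggests that paired values of some kind were already in hand. On this view the defect for the three pressures is an unstated source, not a contradiction. This stands, and it is why the two groups are treated separately here.

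A second reply is that the TAVR wording is a slip for before and after eplerenone. That would restore a pair for the five KCCQ tests, but the text would still need correcting. It would not supply a pair for LVEDP or blood pressure.

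Three smaller points are fair. Item 4 introduces its KCCQ list as inclusive, so eight is the number of named measures and not necessarily of all tests. SAP item 1 is blank in the available text and might have defined time points, although items 2 and 4 are explicit. The stated aims are tolerability and feasibility, which these tests do not measure. None of this makes the KCCQ label correct.

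**Conclusion.** The concern holds, in two parts.

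- **KCCQ, five tests:** the SAP contradicts the protocol. Both scheduled forms follow TAVR, by up to about 104 and 112 weeks under the assumption above, and the only contrast they support is change over the eplerenone period. This must be corrected because it changes which intervention the result describes.
- **LVEDP, systolic and diastolic blood pressure, three tests:** no pair is scheduled under either reading, and the SAP gives neither source nor dates. It also does not say whether its blood pressure is procedural or the 8-week reading. Suitable records may exist, so these tests are undefined rather than shown to be wrong.

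The size of any resulting bias is not estimated; the documents give nothing to estimate it from. The conclusion rests on the explicit wording of SAP items 2 and 4 and on the protocol's stated schedule.

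**What to change.** Amend SAP items 2 and 4 as follows.

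1. **KCCQ-12:** define the contrast as the 8-week score minus the study-baseline score and drop the reference to TAVR.
2. **Systolic and diastolic blood pressure:** choose one of three options. Name the source and dates of a pre-eplerenone reading from existing records to pair with the 8-week value; or, if procedural pressures are meant, label the contrast as procedural and give its source; or report the 8-week value descriptively without a paired test.
3. **LVEDP:** by default, report the post-TAVR value as a baseline characteristic and make no eplerenone comparison with it. If pre-TAVR recordings exist and are used, label the contrast as procedural, state the source, and note that subjects were selected on post-TAVR AVi.

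Because the SAP reads as a report of analyses already done, any result issued under the present labels needs the same correction.

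The KCCQ change costs only rewording, with no new data and no change of test. Keeping a blood pressure or LVEDP pair means a record look-up for up to 25 subjects. The price is that LVEDP, and possibly blood pressure, would have no p-value bearing on eplerenone.
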